6.1 Research Drug Information

Generic name: Febuxostat (febuxostat)

acid Chemical name: 2[-3-cyano-4(-2-methylpropoxy)phenyl]-4-methylthiazole-5-carboxylic acid

Chemical structural formula :

Molecular formula : C₁₆H₁₆N₂O₃S

[figure not shown]
Trade Name: Feburic® Tablets 10 mg, Feburic® Tablets 20 mg, Feburic® Tablets 40 mg

For details, please refer to the attached document and interview form.

Generic name: benz bromarone

Scientific Name: 3 , 5-Dibromo-4-hydroxyphenyl 2-ethylbenzo[b]furan-3-yl ketone

Chemical structural formula:

Molecular formula: C₁₇H₁₂Br₂O₃

Trade Name: Benz bromarone® Tablets 25 mg, Benz bromarone® Tablets 50 mg

For specifics, please refer to the attached document and interview form.

6.2 Anticipated adverse reactions

The following side effects have been reported.

Excerpt from Febuxostat Appendix (Revised November 2013 (5th Edition))

(1) Serious adverse reactions: Hepatic dysfunction (frequency unknown), Hypersensitivity (frequency unknown)

(2) Other side effects

Type \ Frequency	Frequency unknown Note)	Less than 1-5	Less than 1
blood	thrombocytopenia anemia		decreased white blood cell count
endocrine			Increased TSH
nervous system	Headache, taste disorder		Tingling sensation in limbs, floating dizziness, somnolence
heart	pulsation		ECG abnormality
gastrointestinal			Diarrhea, abdominal discomfort, nausea, abdominal pain
Liver and Biliary System		Abnormal liver function test values [increased ALT (GPT), AST (GOT), γ -GTP, etc.].	
skin	urticaria		Rash, pruritus, erythema
musculoskeletal system		arthralgia	Limb pain, limb discomfort, increased CK (CPK)
Renal and urinary tract	decreased urine output		Increased beta-N-acetyl D-glucosaminidase, increased urinary beta2-microglobulin, increased blood creatinine, increased blood urea, frequent urination
Other	swelling		Fatigue, dry mouth, increased triglycerides in the blood, increased CRP

Note 1) Not observed in domestic clinical trials, but observed in foreign countries.

Excerpt from Benzboromarone® Tablets 25 mg, 50 mg (Revised May 2013 (11th Edition))

(1) Serious adverse reactions: Hepatic dysfunction (frequency unknown): Severe hepatic disorders such as fulminant hepatitis and jaundice may occur.

(2) Other side effects

Frequency Type	0.1% or more	Less than 0.1	Frequency unknown
Hypersensitivity ^{Note 1)}	Itchiness, rash, urticaria	Facial redness, erythema	photosensitivity
Liver ^{Note 2)}	Increase in AST (GOT) and ALT (GPT) rise	Increase in Al-P	jaundice
digestive organs	Gastric discomfort, Gastrointestinal disorders, Diarrhea, Soft stools, Heartburn	Stomachache, abdominal pain, nausea, roughness in the mouth	
Other		Edema, cardiac discomfort, headache	

(Note 1) If any of these symptoms occur, the administration should be discontinued.

(Note 2) If such symptoms occur, the administration should be discontinued and appropriate measures should be taken.

7. Outcome variables

7.1 Outcomes

(1) Primary outcome

Percent and absolute change in eGFR between immediately before and 52 weeks (1 year) after initiation of treatment

(2) Subsidiary study outcomes

- 1) Percent and absolute change in eGFR at Week 8 after treatment initiation
- 2) Percent and absolute changes in office blood pressure at 8 & 52 weeks after treatment commencement
- 3) Difference in percent and absolute change in eGFR at 8 & 52 weeks before and after treatment commencement
- 4) Percent and absolute changes in serum uric acid level and rate of attainment of serum uric acid level below 6.0 mg/dL at weeks 8 & 52 after treatment commencement
- 5) P Percent and absolute change in urinary albumin/creatinine ratio at weeks 8&52 after treatment commencement
- 6) Percent and absolute change in urine pH at 8&52 weeks after treatment commencement (%)
- 7) Percent and absolute change in XO activity at 8&52 weeks post-dose commencement (%)
- 8) Percent and absolute change in hs-CRP at 8&52 weeks after treatment commencement (%)
- 9) Percent and absolute change in urinary 8-OHdG (8-hydroxy-2'-deoxyguanosine) at 8 & 52 weeks after treatment commencement (%)
- 10) Percent and absolute change in urinary angiotensinogen at 8&52 weeks after treatment commencement (%)
- 11) Percent and absolute change in urinary L-FABP at 8 & 52 weeks after treatment commencement (%)
- 12) Stratified analysis of primary and secondary outcomes by gender, proteinuria, and renal function

7.2 Statistical analysis

(1) Target population for analysis

Case handling will be assessed by the principal investigator. The largest Full Analysis Set will be presented as the patient population enrolled in the study, who have received at least one study treatment, and whose eGFR has been evaluated before and after the treatment initiation in treatment phase 1.

(2) Statistical analysis

ITT analysis will conduct the analyses. The subject background will be evaluated by

calculating frequency summaries or summary statistics for each allocation group and conducting Student's t-test and Pearson's chi-square test.

The primary endpoint will undergo an unpaired t-test (or non-parametric test in the case of non-normal distribution). For the secondary endpoints, the corresponding t-test (or non-parametric test for non-normal distribution) will be conducted. The rate of attainment of serum uric acid levels of 6.0 mg/dL or less will be compared using Pearson's chi-square test.

For adverse events, the frequency, and prevalence of occurrence will be calculated for each event.

The significance level of the test is 5% two-sided unless otherwise stated. For estimating intervals, 95% confidence intervals are used.

8. What to do in the event of an adverse event

If a negative event is noticed, the treating doctor should act right away to address it and document the progress in the patient's medical file. Adverse events should be reported in the case report form.

Adverse events that fall under the following categories should be reported to the medical institution's leader following the medical institution's regulations as serious adverse events.

- (1) Deadly things
- (2) A threat to life.
- (3) Hospitalization for treatment or extension of hospitalization period
- (4) Permanent or significant disability or malfunction
- (5) Those with congenital anomalies.

9. Informed consent and provision of information to study participants

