4.2 Expected number of participants and implementation period

Expected number of participants: 100 (50 in each of treatment groups A and B)

Research period: After approval by the Ethical Review Committee - February 28, 2021

Research registration period: After approval by the Ethical Review Committee - November 30, 2018

The basis for setting the number of expected participants.

We predicted that a sample size of 100 participants the study would provide 90% power to detect differences in the primary outcome (change in eGFR) of 15 mL/min/1.73m² per year between the randomized groups based on the findings of previous studies,^{14, 15} assuming a standard deviation of 20 mL/min/1.73m², a drop-out rate of 20%, a type I error rate of 5%, and the use of a two-sided significance test.

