11.6 Secondary Use of Information

The potential for secondary use of the data collected for this study for other studies, etc., should be discussed in the explanatory document, and the subject's written consent should be obtained. Before using the data from this study is to be used for unrelated purposes, the study plan must receive the Ethical Review Committee's approval. Subjects who previously gave their consent for this protocol (Version 5.0) will be re-consented for secondary use.

12. Handling of samples and information

The E RED Cap of the Center for Clinical Research Education and Management at the University of the Ryukyus will serve as the study's EDC system. Essential documents related to this study (e.g., copy of application form, notification letter from the hospital director, consent form, case report form, patient identification code, and other documents or records necessary to ensure the accuracy of the data) will be kept in the Department of Cardiovascular, Nephrology, and Neurology, Graduate School of Medicine, University of the Ryukyus, will retain key study records for 5 years following the study' conclusion. Data from patients who withdraw their consent will be destroyed immediately. Blood samples collected and stored for this study will be discarded after the necessary marker measurements are completed.

13. Cost burden for subjects

The cost of measuring the inflammatory markers and oxidative stress needed for this study will be covered by research funds. All additional medications, observations, and tests necessary for this study will be covered by insurance. Therefore, there will be no additional burden on subjects due to participation in the study.

Subjects who partook in the study will be rewarded for their cooperation with rice vouchers worth 3,000 yen at three points: just before the start of the study, at 8 weeks, and 52 weeks.

14. Quality control and reliability assurance

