(7) Change in XO activity from immediately before initiation of randomized treatment (visit2) to 8 & 52 weeks after initiation of treatment (visits 3 & 4) [unit: % / 8 weeks, % / 52 weeks, pmol IXP / min / mL / 8 weeks and pmol IXP / min / mL / 52 weeks]

(8) Change in hs-CRP from immediately before initiation of randomized treatment (visit2) to 8 & 52 weeks after initiation of treatment (visits 3 & 4) [unit: % / 8 weeks, % / 52 weeks, mg / dL / 8 weeks and mg / dL / 52 weeks]

(9) Change in urinary 8-OHdG (8-hydroxy-2'-deoxyguanosine) from immediately before initiation of randomized treatment (visit2) to 8 & 52 weeks after initiation of treatment (visits 3 & 4) [unit: % / 8 weeks, % / 52 weeks, ng / mL / 8 weeks and ng / mL / 52 weeks]

(10) Change in urinary angiotensinogen from immediately before initiation of randomized treatment (visit2) to 8 & 52 weeks after initiation of treatment (visits 3 & 4) [unit: % / 8 weeks, % / 52 weeks, μ g / gCr / 8 weeks and μ g / gCr / 52 weeks]

(11) Change in urinary L-FABP from immediately before initiation of randomized treatment (visit2) to 8 & 52 weeks after initiation of treatment (visits 3 & 4) [unit: % / 8 weeks, % / 52 weeks, μ g / gCr / 8 weeks and μ g / gCr / 52 weeks]

2-7. Sample size estimation

Expected number of participants: 100 (50 in each of treatment groups A and B)

[Rationale for sample size estimation]

The main objective of this study was to exploratively investigate the effect of febuxostat administration and benz bromarone on renal function in patients with hyperuricemia complicated by chronic kidney disease. Based on the results of previous studies, we expected the difference between the two treatments to be eGFR/52W 15 ml/min/1.73m².^{1,2} Then, we calculated α 0.05, power 0.8, δ 15, σ 20, and dropout rate as 20%.

2-8. Follow-up duration

Participants will be followed up for 52 weeks (treatment period 1 for 8 weeks and treatment period 2 for 44 weeks).

2-9. Research period

Research period: from approval by the Ethical Review Committee to February 28, 2021

Registration period : from approval by the Ethical Review Committee to November 30, 2018

3. Analysis population

Full analysis set (FAS): In accordance with the intention to treat (ITT) principle, all patients except for those without information after randomization will be included in the analysis.

Per protocol set (PPS): Sensitivity analysis excluding participants with protocol violation might be conducted.

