5.2. Participant flow

Number of registered participants, randomized participants, analysis population, treatment discontinuation and drop-out will be summarized in Figure (Participant flow) .

Participants who did not receive randomized treatment, those who were excluded after registration, those who discontinued treatment or dropped out will be summarized by reason. Drop-out rate will be estimated as number of participants with discontinuation and drop-out / number of FAS. These results will be included in Figure (Participant flow) .

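### The protocol's Full Analysis Set requires a dose and, on its natural reading, a phase 1 on-treatment eGFR, and so fits neither its own ITT label nor the SAP's definition

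*Protocol*

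**What the plan says.** - **Protocol 7.2(1)**: the FAS consists of enrolled patients "who have received at least one study treatment, and whose eGFR has been evaluated before and after the treatment initiation in treatment phase 1". The same paragraph says "Case handling will be assessed by the principal investigator", with no criteria or timing.
- **Protocol 7.2(2)**: "ITT analysis will conduct the analyses".
- **SAP section 3**: "In accordance with the intention to treat (ITT) principle, all patients except for those without information after randomization will be included in the analysis". There is no dose condition and no eGFR condition.
- **SAP 2-6-1 and 5.4**: the primary endpoint is the change in eGFR from Visit 2 to Visit 4, compared by unpaired t-test or ANOVA. Multiple imputation is a sensitivity analysis if at least 5% of primary outcomes are missing. SAP 4.2 rules out imputation otherwise, in principle.
- **SAP 5.2**: "Drop-out rate will be estimated as number of participants with discontinuation and drop-out / number of FAS".
- **Protocol section 12**: "Data from patients who withdraw their consent will be destroyed immediately". Protocol 4.7(2), by contrast, asks for the date, the reason and the obtainable Visit 3 and Visit 4 results of stopped cases, and 4.7(1)(b) lists withdrawal of consent among the grounds for stopping.

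**The concern.** An analysis set that depends on having been dosed and on having a post-baseline measurement is modified ITT, not ITT. Both conditions are met or missed after randomisation, so they can act differently in the two arms. Week-8 eGFR is a secondary endpoint; it should not decide who enters the week-52 comparison.

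With two definitions in force, whoever runs the analysis must choose between them, and the choice can change which observed week-52 values are used. The set may also determine who is imputed and the base for the 5% missingness trigger, because SAP 5.4 does not say of which set the 5% is taken.

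**Working it through.** **1. The planning figure, for scale.** Inputs from protocol 4.2: "Expected number of participants: 100 (50 in each of treatment groups A and B"), and "90% power to detect differences in the primary outcome (change in eGFR) of 15 mL/min/1.73m² per year", with SD 20, 20% drop-out and two-sided alpha 5%.

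- Evaluable per arm: 50 × 0.8 = 40.
- Power: Φ(15 / (20·√(2/40)) − 1.960) = Φ(3.354 − 1.960) = Φ(1.394) = 91.8%. The t-test gives 91.2%.
- Solving for 90%: n = 2·(1.960 + 1.282)²·(20/15)² = 37.4, so 38 per arm. 38/0.8 = 47.5, so 48 per arm and 96 in total, which rounds up to 100.

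The protocol's figure reproduces. It counts on 40 patients per arm with an observed endpoint, and nothing below changes the sample size.

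**2. The two definitions applied to the same patients.** Visit 3 is the only scheduled on-treatment measurement in phase 1 (protocol 5.1), and only results within 2 weeks of plan are used (SAP 4.1).

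| Randomised patient | Has primary endpoint | Protocol FAS | SAP FAS |
|---|---|---|---|
| Dosed, valid week 8, week 52 present | yes | in | in |
| Dosed, no valid week 8, week 52 present | yes | out (natural reading) | in |
| Never dosed, but followed to week 52 | yes | out | in |
| Dosed, week 8 present, no week 52 | no | in | in |
| No information after randomisation | no | out | out |

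The second and third rows hold patients with the primary endpoint on whom the texts disagree. The third does not depend on how the eGFR clause is read. The last row shows that the SAP's set is not strict ITT either. No document gives a count for rows two and three, and the supplementary result tables at the end of the file show estimates without patient numbers.

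**3. Drop-out rate (reporting only).** Assume 100 randomised and 20 lost as planned, k of them outside the FAS.

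| k | 20/100 | 20/(100−k) | (20−k)/(100−k) |
|---|---|---|---|
| 0 | 20.0% | 20.0% | 20.0% |
| 5 | 20.0% | 21.1% | 15.8% |
| 10 | 20.0% | 22.2% | 11.1% |
| 20 | 20.0% | 25.0% | 0.0% |

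The same 20 losses can be reported as anything from 0% to 25%, depending on when they occur and whether the numerator is also confined to the FAS. Over all randomised patients the rate is always 20% and can be compared with the planning assumption. The values of k are illustrative.

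**The case against.** **The wording allows another reading.** The reference to phase 1 can attach to the start of treatment, which does fall in phase 1. Any later eGFR, including week 52, would then qualify, and the patient who misses week 8 would be in both sets. This stands as a possible reading, though not the more natural one. It leaves the never-dosed patient and the ITT label unresolved.

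**Safeguards exist.** The SAP plans multiple imputation, a GEE analysis of Visits 3 and 4 and a possible per-protocol analysis. The protocol asks for data after discontinuation where obtainable. These soften the effect, but none says which FAS governs.

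**Stronger readings that the documents do not support:**

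- A reader might infer that leaving, say, 5 of 50 patients (10% of an arm) out of the FAS biases the primary result to that extent. If those patients have no information after randomisation, they have no change score and cannot enter the unimputed t-test under any definition.
- A reader might infer that the principal investigator's role contradicts ITT, or that exclusions will be made knowing the arm. Treating physicians do receive the allocation (protocol 4.3), and no blinding is described. But nothing says when, or with what information, the principal investigator decides. What stands is discretion without a stated rule.
- A reader might infer that early losses disappear from the report. SAP 5.2 also requires the numbers randomised and analysed, and the reasons for exclusion and drop-out, so the rate over all randomised can be recovered.
- A reader might infer from section 12 that withdrawers are certain to be lost from the efficacy and safety counts. Destroying their data could leave them without post-randomisation information, but the section conflicts with protocol 4.7(2) and SAP 5.2, and the consent pages are not in the copy reviewed.

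**Conclusion.** The conflict is real and wrong as written: one file holds two FAS definitions, and the narrower one carries an ITT label that it does not meet. It can exclude randomised patients whose primary endpoint was observed. Its size is unknown, because it equals the number of patients with Visit 2 and Visit 4 eGFR who were never dosed or have no valid phase 1 on-treatment value. The second group counts only on the natural reading of the clause. For never-dosed patients, the conclusion assumes that they are followed and that their week 52 can be dated, since the schedule counts from the start of drug.

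Two further points are secondary. The drop-out denominator affects reporting, not the primary test. The destruction of withdrawers' data is an unreconciled tension with the rules for recording and summarising stopped cases.

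**What to change.** - **One definition in both texts.** FAS = all randomised patients, analysed as allocated. Delete the dose and phase 1 eGFR conditions from protocol 7.2. If the narrower set is kept, call it modified ITT and make it secondary.
- **Keep the primary test.** The t-test or ANOVA uses every patient with Visit 2 and Visit 4 eGFR. The multiple imputation in SAP 5.4 covers all randomised patients as sensitivity analysis. State how week 52 is dated for a patient who never started drug.
- **Case handling.** Write down the exclusion rules and have them applied before data lock by people without access to allocation.
- **Drop-out.** Report it over all randomised patients, per arm.
- **Withdrawal of consent.** Reconcile protocol section 12 with protocol 4.7(2) and SAP 5.2, keeping data collected before withdrawal where consent allows.

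The cost is wording in the protocol and SAP, possibly a sentence in the consent document, and someone without access to allocation to review cases. Sample size, visits and primary test do not change. Some FAS patients will contribute baseline data only.

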9.1 Explanation to the patient

Before patient registration, the attending physician should give the patient an explanation document authorized by the Ethical Review Committee and verbally explain the following details.

- (1) Conducting the research
- (2) Purpose of this study
- (3) Duration of this study
- Subjects of this study
- 5) Method of this study
- 6) About the flow of this research
- ⑦ Expected results of this study.
- ⑧ Advantages and disadvantages of the participants in this study
- (ix) Cost sharing for this research.
- (10) Health hazards during participation in this study
- 11) Freedom to participate in this research and withdrawal
- ⑫ Handling of personal information and research results
- ⑬ Conflict of interest
- Monitoring and auditing
- (xv) Contact information and contact details of the physician in charge

9.2 Obtaining Consent

The responsible physician will use the patient information document to verbally explain the research's contents to the candidate patient, give them time to consider it, and then ask them to participate in the study once they are sure they understand it completely. The consent form is signed by the patient if they consent to participate in the research. Verify that the consent form includes the name of the doctor who provided the explanation, the explanation's date, the patient's name who received the explanation and consented, and the date the consent was obtained. Make a copy of the consent form and give the patient. The original should be kept in the patient's medical file or another location specified by the hospital.

If during research participation information is learned that might influence a subject's decision to continue participating in the study or not, the information must be immediately explained to the subject, the subject's decision to continue participating in the study must be reaffirmed, and

this must be documented in the medical file. Every time the patient explanation document is updated, the subjects' written consent to continue participation in the study will be required.

9.3 Withdrawal of Consent

Even if a subject consents to participate in the study, he, or she has the right to leave at any time, for any reason. In such a situation, the physician in charge of the subject will give the best medical care attainable so that the subject will not suffer any kind of disadvantage.

10. Benefits and disadvantages of subjects

10.1 Profit

Due to the short duration of participation in the study, there will be no immediate benefits for the subjects, but the study may offer helpful information for the treatment and management of patients with hyperuricemia complicating chronic kidney disease.

10.2 Disadvantages

Although the study drugs (benzbromarone and febuxostat) are commonly used in daily practice as one of the uric acid production inhibitors, will be used in this study within the limits of the approved doses in this study, there is a possibility that the adverse reactions listed in "6.2 Expected adverse reactions" may occur. However, some of the negative effects listed in "6.2 Expected adverse reactions" might manifest. These adverse events may also occur in routine clinical practice, and participation in the study is not anticipated to increase the risk of adverse reactions.

The physician in charge will conduct the study with the highest priority on ensuring the safety of the subjects, and will promptly take appropriate measures to address any adverse events.

11. Ethical consideration

